Walsh JK & Schweitzer PK. Ten-year trends in the pharmacologic treatment of insomnia. *Sleep*. 1999; 22:371-375.

8.0

STUDY OBJECTIVES

The objectives of this study seeks to evaluate and compare the effectiveness of (1) cognitive behavior therapy for insomnia [CBT-I], (2) focus of attention [FOA], (3) a combination of cognitive behavior therapy for insomnia and focus of attention, and (4) a sleep hygiene control intervention.

PRIMARY OBJECTIVE The primary objective is completion of 6 treatment sessions and completion of the 3 months, 6 months and 12 months follow-up assessment. Improvement of insomnia outcome is measured by Self Report Sleep Measures (SRSM).

SECONDARY OBJECTIVE The Secondary objective is improvement outcomes.

SAFETY AND TOLERABILITY END POINTS

In general the potential risks for participants are minimal. The treatment approaches involved in related studies have been shown to be a safe procedure and in most of the published studies people who underwent these procedures did not report any harmful effects. It is nonetheless possible participant(s) may experience some discomforts during the treatment. These may include temporary decrease in time asleep and accompanying daytime drowsiness. Some people may become anxious while initially following the treatment procedures, with increased worry about their sleep difficulty. Anxiety and worry about sleep difficulty are in fact common among persons with insomnia. Therefore identifying and addressing these possibilities will be directly addressed during the treatment, and participants will be given guidance about what to expect and how to manage should these discomforts occur. Persons with certain medical illnesses, certain psychiatric illnesses or other sleep disorders may be at increased potential risk of exacerbation of that illness. This is a possibility for participants with epilepsy, bipolar depression, parasomnias, obstructive sleep apnea or other illnesses which have excessive daytime sleepiness as a feature of the parent disorder. The participant may (or may not) be assigned to a treatment which involves sleep restriction. Sleep loss through sleep restriction may

- 1) Lower the threshold for seizures in persons with epilepsy;
- 2) Precipitate mania in bipolar participants;
- 3) Exacerbate parasomnias;
- 4) Prevent adequate ventilation in patients with obstructive sleep apnea; and/or
- 5) Aggravate the day time somnolence to the point where it is no longer safe for the participant to drive, operate machinery and/or make judgments that adequately promote their own and/or the safety and well-being of others.

The risk is generally higher when these illnesses are untreated. Prospective participants treated for any of these illnesses and interested in participating must have the written approval of their treatment provider in order to be eligible. Prospective participants will be screened and informed of these potential risks. If any of these risks (1-5 above) occur during the study, the participant will be asked to immediately discontinue the sleep restriction, and an alternative treatment not involving sleep restriction will be offered. The participant will also have the option of discontinuing the treatment if they prefer this to proceeding with the alternative treatment which does not involve sleep restriction.

SAMPLE SIZE

It is estimated that 320 prospects will need to be screened in order to have 40 per group for a total of 160 participants.

ANALYSIS POPULATIONS

Safety Population: will include all randomized subjects who meet eligibility criteria and meet with their treatment provider for session 1.

Intent-to-Treat Population: will include all subjects who meet with their treatment provider for session 1 and for whom the treatment provider determines the subject meets diagnostic criteria for 780.52 Insomnia Disorder.

Pre-Protocol (PP) Population: will include all subjects who complete the 6 sessions of treatment as well as the 3 month, 6 month and 12 month follow up assessment. It is estimated that 80% of those who complete session 1 will complete session 6. It is estimated that 80% of those who complete session 6 will complete the 3 month, 6 month and 12 month follow up assessments. This will result in 25 participants who will have completed the entire study.

HYPOTHESES

Hypothesis 1: Treatment Effect on Subjective Measures from Weekly Sleep Log

There will be no statistically significant overall post-treatment minus pre-treatment differences across the four treatment groups in subjective sleep measures using standardized sum scores across the four measures of self-report data from Weekly Sleep Log. If ANOVA indicates a significant overall difference, pairwise t-tests will test the following hypotheses:

Hypothesis 1a. There will be no statistically significant post-treatment minus pre-treatment mean differences across the four treatment groups in the mean number of minutes to initiate sleep (SL);

Hypothesis 1b. There will be no statistically significant post-treatment minus pre-treatment differences across the four treatment groups in the mean number of minutes to return to sleep upon awakening after sleep onset (WASO);

Hypothesis 1c. There will be no statistically significant post-treatment differences across the four treatment groups in the mean total number of minutes of sleep (TST);

Hypothesis 1d. There will be no statistically significant post-treatment minus pre-treatment differences across the four treatment groups in the mean total number of minutes of sleep divided by the total number of minutes in bed (SE).

Hypothesis 2: Treatment Effect on Objective Measures of Sleep

There will be no statistically significant overall post-treatment minus pre-treatment differences across the four treatment groups in overall objective sleep measures using standardized sum scores for data from subjects wearing an ActiWatch 2. If ANOVA indicates a significant overall difference, pairwise t-tests will test the following hypotheses:

Hypothesis 2a. There will be no statistically significant post-treatment minus pre-treatment mean differences across the four treatment groups in the mean number of minutes to initiate sleep (SL);

Hypothesis 2b. There will be no statistically significant post-treatment minus pre-treatment differences across the four treatment groups in the mean number of minutes to return to sleep upon awakening after sleep onset (WASO);

Hypothesis 2c. There will be no statistically significant post-treatment minus pre-treatment differences across the four treatment groups in the mean total number of minutes of sleep (TST);

Hypothesis 2d. There will be no statistically significant post-treatment minus pre-treatment differences across the four treatment groups in the mean total number of minutes of sleep divided by the total number of minutes in bed (SE).

Hypothesis 3: Treatment Effect on Insomnia Severity

There will be no statistically significant post-treatment minus pre-treatment mean differences across the four treatment groups in insomnia severity as measured by the Insomnia Severity Index (ISI).

Hypothesis 4: Treatment Effect on Insomnia Diagnosis

There will be no statistically significant (chi square) post-treatment minus pre-treatment mean differences across the four treatment groups in the percentage of subjects who meet DSM-5 criteria for 780.52 Insomnia Disorder across time (pre-treatment; post-treatment).

Hypothesis 5: Treatment Effect on Self Report Sleep Satisfaction Measures

There will be no statistically significant overall post-treatment minus pre-treatment differences across the four treatment groups in overall satisfaction/dissatisfaction with sleep using standardized sum scores for data from subjects across the five likert scale measures of satisfaction/dissatisfaction on the Self Report Sleep Measures.

If ANOVA indicates a significant overall difference, pairwise t-tests will test the following hypotheses:

Hypothesis 5a. There will be no statistically significant post-treatment minus pre-treatment mean differences across the four treatment groups in self report of extent of satisfaction or dissatisfaction with ability to get to sleep at bedtime;

Hypothesis 5b. There will be no statistically significant post-treatment minus pre-treatment mean differences across the four treatment groups in self report of extent of satisfaction or dissatisfaction with frequency of awakenings after having initiated sleep;

Hypothesis 5c. There will be no statistically significant post-treatment minus pre-treatment mean differences across the four treatment groups in self report of extent of satisfaction or dissatisfaction with ability to return to sleep after awakenings during the night;

Hypothesis 5d. There will be no statistically significant post-treatment minus pre-treatment mean differences across the four treatment groups in self report of extent of satisfaction or dissatisfaction with average quantity of sleep;

Hypothesis 5e. There will be no statistically significant post-treatment minus pre-treatment mean differences across the four treatment groups in self report of extent of satisfaction or dissatisfaction with overall quality of sleep.

Hypothesis 6: Treatment Effect on Subjective Sleep Distress

There will be no statistically significant post-treatment minus pre-treatment mean differences across the four treatment groups in self report of extent of distress with sleep difficulty.

Hypothesis 7: Treatment Effect on Subjective Report of Impairment

There will be no statistically significant overall post-treatment minus pre-treatment differences across the four treatment groups in overall self-report of impairment due to sleep difficulty measures using standardized sum scores across the three measures. If ANOVA indicates a significant overall difference, pairwise t-tests will test the following hypotheses:

Hypothesis 7a. There will be no statistically significant post-treatment minus pre-treatment mean differences across the four treatment groups in self report of extent of social impairment due to sleep difficulty;

Hypothesis 7b. There will be no statistically significant post-treatment minus pre-treatment mean differences across the four treatment groups in self report of extent of occupational impairment due to sleep difficulty;

Hypothesis 7c. There will be no statistically significant post-treatment minus pre-treatment mean differences across the four treatment groups in self report of extent of academic impairment due to sleep difficulty.

Hypothesis 8: Endurance of Treatment Effect on Subjective Measures from Weekly Sleep Log

There will be no statistically significant overall 12 month follow up minus pre-treatment differences across the four treatment groups in subjective sleep measures using standardized sum scores across the four measures of self-report data from Weekly Sleep Log. If ANOVA indicates a significant overall difference, pairwise t-tests will test the following hypotheses:

Hypothesis 8a. There will be no statistically significant 12 month follow up minus pre-treatment mean differences across the four treatment groups in the mean number of minutes to initiate sleep (SL);

Hypothesis 8b. There will be no statistically significant 12 month follow up minus pre-treatment differences across the four treatment groups in the mean number of minutes to return to sleep upon awakening after sleep onset (WASO);

Hypothesis 8c. There will be no statistically significant 12 month follow up minus pre-treatment differences across the four treatment groups in the mean total number of minutes of sleep (TST);

Hypothesis 8d. There will be no statistically significant 12 month follow up minus pre-treatment differences across the four treatment groups in the mean total number of minutes of sleep divided by the total number of minutes in bed (SE).

Hypothesis 9: Endurance of Treatment Effect on Objective Measures

There will be no statistically significant overall significant overall 12 month follow up minus pre-treatment differences across the four treatment groups in overall objective sleep measures using standardized sum scores for data from subjects wearing an ActiWatch 2.

If ANOVA indicates a significant overall difference, pairwise t-tests will test the following hypotheses:

Hypothesis 9a. There will be no statistically significant post-treatment minus pre-treatment differences across the four treatment groups in each of the following objective sleep measures using data from subjects wearing an ActiWatch 2:

Hypothesis 9b. There will be no statistically significant 12 month follow up minus pre-treatment mean differences across the four treatment groups in the mean number of minutes to initiate sleep (SL);

Hypothesis 9c. There will be no statistically significant 12 month follow up minus pre-treatment differences across the four treatment groups in the mean number of minutes to return to sleep upon awakening after sleep onset (WASO);

Hypothesis 9d. There will be no statistically significant 12 month follow up minus pre-treatment differences across the four treatment groups in the mean total number of minutes of sleep (TST);

Hypothesis 9e. There will be no statistically significant 12 month follow up minus pre-treatment differences across the four treatment groups in the mean total number of minutes of sleep divided by the total number of minutes in bed (SE).

Hypothesis 10: Endurance of Treatment Effect on Insomnia Severity

There will be no statistically significant 12 months follow up minus pre-treatment mean differences across the four treatment groups in insomnia severity as measured by the Insomnia Severity Index (ISI).

Hypothesis 11: Endurance of Treatment Effect on Insomnia Diagnosis

There will be no statistically significant chi square 12 month follow up minus pre-treatment mean differences across the four treatment groups in the percentage of subjects who meet DSM-5 criteria for 780.52 Insomnia Disorder across time (pre-treatment; post-treatment; 12 month follow-up).

Hypothesis 12: Endurance of Treatment Effect on Sleep Satisfaction Measures

There will be no statistically significant overall 12 month follow up minus post-treatment differences across the four treatment groups in overall satisfaction/ dissatisfaction with sleep using standardized sum scores for data from subjects across the five likert scale measures of satisfaction/dissatisfaction on the Self Report Sleep Measures.

If ANOVA indicates a significant overall difference, pairwise t-tests will test the following hypotheses:

Hypothesis 12a. There will be no statistically significant 12 month follow up minus post-treatment mean differences across the four treatment groups in self report of extent of satisfaction or dissatisfaction with ability to get to sleep at bedtime;

Hypothesis 12b. There will be no statistically significant 12 month follow up minus post-treatment mean differences across the four treatment groups in self report of extent of satisfaction or dissatisfaction with frequency of awakenings after having initiated sleep;

Hypothesis 12c. There will be no statistically significant 12 month follow up minus post-treatment mean differences across the four treatment groups in self report of extent of satisfaction or dissatisfaction with ability to return to sleep after awakenings during the night;

Hypothesis 12d. There will be no statistically significant 12 month follow up minus post-treatment mean differences across the four treatment groups in self report of extent of satisfaction or dissatisfaction with average quantity of sleep;

Hypothesis 12e. There will be no statistically significant 12 month follow up minus post-treatment mean differences across the four treatment groups in self report of extent of satisfaction or dissatisfaction with overall quality of sleep.

Hypothesis 13: Endurance of Treatment Effect on Subjective Sleep Distress

There will be no statistically significant 12 month follow up minus post-treatment mean differences across the four treatment groups in self report of extent of distress with sleep difficulty.

Hypothesis 14: Endurance of Self Report Sleep Satisfaction Measures

There will be no statistically significant overall 12 month follow up minus post-treatment differences across the four treatment groups in overall satisfaction/ dissatisfaction with sleep using standardized sum scores for data from subjects across the five likert scale measures of satisfaction/dissatisfaction on the Self Report Sleep Measures.

If ANOVA indicates a significant overall difference, pairwise t-tests will test the following hypotheses:

Hypothesis 14a. There will be no statistically significant 12 month follow up minus post-treatment mean differences across the four treatment groups in self report of extent of satisfaction or dissatisfaction with ability to get to sleep at bedtime;

Hypothesis 14b. There will be no statistically significant 12 month follow up minus post-treatment mean differences across the four treatment groups in self report of extent of satisfaction or dissatisfaction with frequency of awakenings after having initiated sleep;

Hypothesis 14c. There will be no statistically significant 12 month follow up minus post-treatment mean differences across the four treatment groups in self report of extent of satisfaction or dissatisfaction with ability to return to sleep after awakenings during the night;

Hypothesis 14d. There will be no statistically significant 12 month follow up minus post-treatment mean differences across the four treatment groups in self report of extent of satisfaction or dissatisfaction with average quantity of sleep;

Hypothesis 14e. There will be no statistically significant 12 month follow up minus post-treatment mean differences across the four treatment groups in self report of extent of satisfaction or dissatisfaction with overall quality of sleep.

Hypothesis 15: Satisfaction with Treatment

There will be no statistically significant differences across treatment types in post-treatment reported overall level of satisfaction with the treatment received as measured with a 5-point Likert Scale on the FEEDBACK QUESTIONNAIRE.

Hypothesis 16: Likelihood to Recommend to Others

There will be no statistically significant differences across treatment types in post-treatment reported level of likelihood to recommend to others the treatment received as measured with a 5-point Likert Scale on the FEEDBACK QUESTIONNAIRE.

MISSING DATA

All data measures will be reviewed upon receipt to ensure no data is missing. Subjects who have not completed the data measures and/or specific items will be asked to do so immediately upon the review having identified missing data. In any situations in which important missing data cannot be gathered, the subject will be eliminated from the study. It is anticipated that in effect 5-10% of subjects will not

complete 12 month follow-up. These subjects will then be eliminated as relates to analyses involving 12 month follow-up data. Statistical analyses will be conducted to determine whether those with missing data differ significantly from those without missing data using t test comparing the two groups on total scores on Insomnia Severity Index at pre-treatment as well as post-treatment.

STATISTICS

Repeated measures analysis of variance (2 X 4 ANOVA) will be used to test the Hypotheses 1-3, 5-10 and 11-16. Any statistically significant ANOVAs will be followed by pairwise t-test comparisons to identify between group differences. Chi square will be used to test Hypotheses 4 and 11.

SAFETY ANALYSIS

In general the potential risks for participants are minimal. The treatment approaches involved in related studies have been shown to be a safe procedure and in most of the published studies people who underwent these procedures did not report any harmful effects.

Prospective participants will be informed that it is nonetheless possible you may experience some discomforts during the treatment. These may include temporary decrease in time asleep and accompanying daytime drowsiness. Some people may become anxious while initially following the treatment procedures, with increased worry about their sleep difficulty. Anxiety and worry about sleep difficulty are in fact common among persons with insomnia. Therefore identifying and addressing these possibilities will be directly addressed during the treatment, and participants will be given guidance about what to expect and how to manage should these discomforts occur. Prospective participants will also be informed that persons with certain medical illnesses, certain psychiatric illnesses or other sleep disorders may be at increased potential risk of exacerbation of that illness. This is a possibility for participants with epilepsy, bipolar depression, parasomnia, obstructive sleep apnea or other illnesses which have excessive daytime sleepiness as a feature of the parent disorder. The participant may (or may not) be assigned to a treatment which involves sleep restriction. Sleep loss through sleep restriction may

- 1) Lower the threshold for seizures in persons with epilepsy;
- 2) Precipitate mania in bipolar participants;
- 3) Exacerbate parasomnias;
- 4) Prevent adequate ventilation in patients with obstructive sleep apnea; and/or
- 5) Aggravate the day time somnolence to the point where it is no longer safe for the participant to drive, operate machinery and/or make judgments that adequately promote their own and/or the safety and well-being of others.

The risk is generally higher when these illnesses are untreated. Prospective participants treated for any of these illnesses and interested in participating must have the written approval of their treatment provider in order to be eligible. If any of these risks (1-5 above) occur during the study, the participant will be asked to immediately discontinue the sleep restriction, and an alternative treatment not involving sleep restriction will be offered. The participant will also have the option of discontinuing the treatment if they prefer this to proceeding with the alternative treatment which does not involve sleep restriction.

9.0

INVESTIGATIONAL PLAN

9.1

OVERALL STUDY DESIGN AND PLAN: DESCRIPTION

TELEPHONE PRE-SCREENING

- A) Provide information about the study, what to expect and what is required if participating. Use Informed Consent form as an outline and a reference. Ask if the person has any questions.
- B) Assess: Inclusion and Exclusion Criteria
The definition of insomnia will be that of DSM-5.

9.1.1

IN PERSON SCREENING AND DATA GATHERING

Complete diagnostic interview per DSM-5. To be eligible, the person must meet the DSM-5 diagnostic criteria for 780.52 Insomnia Disorder. This includes a cumulative minimum average sum of 30 minutes or more of time spent, adding number of minutes of inability to initiate or return to sleep plus number of minutes of early morning awakening with inability to return to sleep.

If the person does not meet diagnostic criteria, thank them for their interest and inform the person that they are not eligible. Provide the specific reason for ineligibility. For example, the person may not meet one or more required aspect of the diagnostic criteria for Insomnia Disorder per DSM-5.

If the person meets eligibility criteria and DSM-5 diagnostic criteria for insomnia disorder, provide the person with a copy of the Informed Consent form. Have the person follow along as you read the form aloud in their presence.

At the end of this process, if the person is still interested in participating, go through the **Informed Consent Form (ICF) for Participants in Insomnia Study** with the participant.

9.1.2

DSM-5 DIAGNOSTIC SCREENING INTERVIEW

Once the Informed Consent form has been completed, the next step involves a diagnostic interview to assess for Insomnia Disorder. The Research Coordinator reads the bold print script to the prospective participant. See DSM-5 Diagnostic Assessment Interview.

QUESTIONNAIRE AND INVENTORIES

Since this is a clinical research trial, we have a questionnaire and some inventories for you to complete as part of the initial data gathering.

Here is the first one. Give the person the Sleep Measures (SM) questionnaire.

I recommend you use a pencil so you can erase if you make an error. Do you need a pencil?
Be sure the person has a comfortable place to write (a table top, for example).

This is the first one. Go ahead. Take a few minutes to complete it. I'm here if you have any questions.

When the participant has completed the Sleep Measures (SM) questionnaire, check to ensure that all questions have been answered. Be sure questions with numerous options (a-f; -3 to +3; etc.) are clearly answered.

Ask the person to complete the **Insomnia Severity Index (ISI)**.

This will give us important information about your insomnia.

When the participant has completed the inventory, check to ensure that all questions have been answered clearly. Check for ISI > or = 10. If not, the person is not eligible. If still eligible, record their score.

Ask the person to complete the **Beck Depression Inventory (BDI)**.

Depression may or may not be a factor for you. However, this is a research study, and the researchers want to be able to assess whether the treatment effect differs by level of depression.

When the participant has completed the BDI, check to ensure that all questions have been answered clearly. Check for BDI > or = 29. If so, the person is not eligible. If still eligible, record their score.

Similarly explain and ask the person to complete the **Beck Anxiety Inventory (BAI)**. When the participant has completed the BAI, check to ensure that all questions have been answered clearly. Check for BAI > or = 36. If so, the person is not eligible. If still eligible, record their score.

1. **Goal Motivation Scale (GMS)**
2. **Goal Motivation Scale-Insomnia (GMS-I)**
3. **Self-Report Sleep Measures (SRSM)**
4. **Clinical Global Impression (CGI)**
5. **Clinical Global Impression – Severity scale (CGI-S)**
6. **Quality of Life Enjoyment and Satisfaction (Q-LES)**
7. **Columbia Suicide Severity Rating Scale (C-SSRS)**

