17). The cognitive therapy component identifies negative sleep talk such as “I can’t stand it that I’m not getting to sleep” or “If I don’t get 8 hours of sleep tonight, I’ll do poorly at work and I could get fired”. Some cognitive therapists have a didactic focus. Others use a variety of cognitive restructuring procedures. While the therapies differ in approach, all are based on the observation that persons with insomnia have negative thoughts and beliefs about their condition and its consequences (Perlis, p. 18). Relaxation therapy focuses on managing stress, muscle relaxation and bedtime rituals that facilitate calming [<https://stanfordhealthcare.org/medical-treatments/c/cognitive-behavioral-therapy-insomnia.html>].

EFFECTIVENESS OF CBT-I:

The results using CBT-I among subjects with primary insomnia reporting sleep onset problems have been moderately effective for treating sleep onset problems. In a meta-analysis of 37 studies, Wu, Appleman, Salazar and Ong (2015) reported 36% of CBT-I patients were in remission from insomnia and no longer met diagnostic criteria for Insomnia Disorder at post-treatment evaluation compared to 16.9% in comparison conditions.

Key quantitative measures include sleep latency, the amount of time it takes person to initiate sleep upon retiring to bed; wake time after sleep onset (WASO); total sleep time (TST); and sleep efficiency, the percentage of sleep period during which person is actually asleep. In their review of the results of five randomized clinical trials which compared CBT-I to medications among patients with primary insomnia, Mitchell, Gehman, Perlis and Umscheid (2012) report sleep efficiency improved 8 to 16 percent with CBT-I. CBT-I generally led to improvement of 30 to 45 minutes in sleep latency and 30 to 60 minutes in total sleep time. Note that TST is not only an outcome variable but is manipulated as part of CBT-I using the restriction of time spent in bed. Sleep restriction therapy requires that time in bed be reduced to a time interval equal to the patient’s ‘sleep ability’ by measuring average TST with a sleep log during a baseline period. As noted by Mitchell, Gehrmann, Perlis and Umscheid, “The net result of this, after completion of CBT-I, is that many patients do not recover their baseline TST but are nevertheless substantially improved with respect to other aspects of sleep” (p. 6).

LIMITATIONS OF COGNITIVE BEHAVIOR THERAPY FOR INSOMNIA:

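### The gating sum of SL, WASO, TST and SE (Hypotheses 1, 2, 8 and 9) has no sign alignment, so similar gains cancel; separately, Hypothesis 7 sums three items of which two are asked only of some participants

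*Protocol*

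**What the plan says.** **Sleep-log and ActiWatch gates.** Protocol Section 8.0, Hypothesis 1, compares the four groups on change from pre- to post-treatment "using standardized sum scores across the four measures of self-report data from Weekly Sleep Log". Sub-hypotheses 1a to 1d name the measures: SL, WASO, TST and SE. They are reached through a gate: "If ANOVA indicates a significant overall difference, pairwise t-tests will test the following hypotheses". Hypothesis 8 repeats this at 12 months: "There will be no statistically significant overall 12 month follow up minus pre-treatment differences across the four treatment groups in subjective sleep measures", with the same score and sub-hypotheses 8a to 8d. Hypotheses 2 and 9 use a standardized sum of ActiWatch data and gate tests of the same four quantities.

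**Direction of benefit.** The Introduction (Effectiveness of CBT-I) reports that "CBT-I generally led to improvement of 30 to 45 minutes in sleep latency and 30 to 60 minutes in total sleep time" and that "sleep efficiency improved 8 to 16 percent with CBT-I". It also says that "many patients do not recover their baseline TST but are nevertheless substantially improved with respect to other aspects of sleep". No section says that any measure is reversed before summing.

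**Hypothesis 7.** The gate is a standardized sum over three impairment measures; 7a to 7c name them as social, occupational and academic. In Appendix IX everyone answers the social item (VII), only employed participants the occupational item (VIII), and only full- or part-time students the academic item (IX). Eligibility (Section 9.3.1) requires neither employment nor study. The Missing Data paragraph of Section 8.0 eliminates a subject when important data cannot be obtained, and does not mention items that do not apply.

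**The concern.** Standardizing changes a measure's location and scale, not its sign. A treatment that shortens SL and WASO pushes the sum down, and the same treatment's gains in TST and SE push it up. One that helps on all four measures by similar amounts can therefore look like sleep hygiene on the gate. The component tests would then not be run, although each could show a difference. Once a gate is passed, the component tests still show direction, so the harm is a false null at the gate.

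For Hypothesis 7 the question is who is analysed. A literal three-item sum exists only for people who are both employed and studying. The social item, which everyone can answer, is tested only after that gate.

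**Working it through.** **Inputs from the protocol.** There are 40 participants per group. Section 8.0, Analysis Populations, says "It is estimated that 80% of those who complete session 1 will complete session 6", assumes a further 80% through follow-up, and concludes "This will result in 25 participants who will have completed the entire study". The arithmetic is 40 x 0.8 = 32 and 40 x 0.8 x 0.8 = 25.6, so the 25 fits a count per group. The Missing Data paragraph instead expects 5 to 10% not to complete 12 months: 40 x 0.95 = 38 and 40 x 0.90 = 36.

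**Assumptions (the protocol gives no alpha, effect size, SD or correlation for these scores).** Alpha is 0.05. Each of three active arms is 0.5 SD of change better than control on SL, WASO and SE; the TST gain t is varied. Every pair of measures has correlation r = 0.2, 0.5 or 0.7 once all point towards improvement.

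**Shift in the sum, active minus control.**
- Unsigned: -0.5 - 0.5 + t + 0.5 = t - 0.5. At t = 0.5 this is 0.
- Aligned: 0.5 + 0.5 + t + 0.5 = 1.5 + t. At t = 0.5 this is 2.0.

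**Variance of the sum.** In raw direction, two pairs correlate +r and four pairs -r.
- Unsigned: 4 + 2(2r - 4r) = 4 - 4r.
- Aligned: 4 + 2(6r) = 4 + 12r.

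**Gate power.** This is a one-way ANOVA on change with four arms. With three arms shifted by delta and one at 0, the noncentrality is n x delta^2 x (3 x 1/16 + 9/16) / Var = 0.75 x n x delta^2 / Var, on 3 and 4n - 4 degrees of freedom. Example: n = 40, t = 0.5, r = 0.5, aligned gives 0.75 x 40 x 4 / 10 = 12.0 and power 83%; unsigned gives 0 and 5%.

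At 40 per arm, for r = 0.2 / 0.5 / 0.7:

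| TST gain (SD) | Unsigned, % | Aligned, % |
|---|---|---|
| +0.5 | 5 / 5 / 5 | 96 / 83 / 73 |
| +0.25 | 9 / 11 / 16 | 90 / 71 / 61 |
| 0 | 22 / 33 / 53 | 77 / 56 / 47 |
| -0.25 | 45 / 67 / 89 | 60 / 41 / 33 |

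With TST +0.5 SD at other sample sizes, the unsigned gate stays at 5%:

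| Per arm | Basis | Aligned, % |
|---|---|---|
| 32 | reach session 6 | 91 / 73 / 62 |
| 38 | 12 months, 5% loss | 95 / 81 / 71 |
| 36 | 12 months, 10% loss | 94 / 78 / 68 |
| 25 | 12 months, per-protocol completers | 81 / 60 / 50 |

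**Hypothesis 7.** Assume 50 to 70% are employed and 5 to 20% are students.
- *Literal sum.* If the two are independent, 160 x 0.5 x 0.05 = 4 to 160 x 0.7 x 0.2 = 22 (22.4) participants have all three items. With maximal overlap the range is 160 x 0.05 = 8 to 160 x 0.2 = 32. Even at 32 (8 per arm), with 0.5 SD per item, shift 1.5 and variance 3 + 6r, power is 26 / 19 / 16%.
- *Sum of applicable items.* A simulation at 40 per arm with the same shares gives 60 to 81%, against 66 to 79% for the mean of applicable items. The social item alone (shift 0.5, variance 1) gives 61%. Little power is lost, but a 0.5 SD gain per item adds 0.5 to the sum for someone neither employed nor studying and 1.5 for an employed student.

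**The case against.** **Silence rather than error.** Reverse-scoring is routine, and an SAP not shown here could add it; no section states a wrong sign. That much stands: a reader might infer that the protocol specifies a mis-signed score, and it does not. But it does fix the score, its components and the gate within the hypotheses, and that rule followed as written gives the cancellation.

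**The 5% figure is one pattern.** This also stands. A reader might infer that these gates can never detect anything, and the documents do not support that. Exact cancellation needs equal standardized gains on all four measures, and the Introduction says many CBT-I patients do not recover baseline TST. With TST at -0.25 SD and r = 0.5, the unsigned gate has 67% power at 40 per arm against 41% aligned. If only SL and WASO gain 0.5 SD, it has 72 / 91 / 99% against 41 / 27 / 22%. Yet the same section also reports a TST gain of 30 to 60 minutes, and at +0.25 SD the unsigned gate is still weak. A gate that gains power as TST worsens penalizes the treatment that helps on every measure.

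**Hypothesis 7 needs the strictest reading to do harm.** Largely conceded. A reader might infer that most participants would be eliminated. An item never due is not naturally missing data, and the Missing Data paragraph does not say that it is. What remains is the conflict between Hypothesis 7 and Appendix IX, with no rule to settle it.

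**Conclusion.** The concern holds for Hypotheses 1, 2, 8 and 9 as a scoring rule that fails as worded when the four measures improve by similar amounts. Under the stated assumptions with TST +0.25 to +0.5 SD, gate power at 40 per arm is about 5 to 16% unsigned and 61 to 96% aligned. For Hypothesis 8 with TST +0.5 SD, aligned power is 50 to 81% at 25 per arm or about 68 to 95% at 36 to 38 per arm, depending on which of the protocol's attrition figures applies; unsigned it is 5% in either case. Where TST is flat or falls, the loss is partial or reversed, and the score then has no direction that means better.

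For Hypothesis 7 the finding is a contradiction about who is analysed, not a demonstrated loss of power. All effect sizes, correlations and employment or student shares are assumptions. Hypotheses 3, 5, 12 and 14 are not part of this point. The correction should be made before analysis.

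**What to change.** **Hypotheses 1, 2, 8 and 9:** state that the SL and WASO z-scores are multiplied by -1 before summing, so that a higher score means better sleep. The downside is lower gate power than the unsigned sum if TST falls (41% against 67% in the case above).

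**Hypothesis 7:** define the score as the mean of the standardized items that apply to the participant. In the Missing Data paragraph, state that a not-applicable item is not missing data and does not trigger elimination.

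The cost is a few lines in the hypotheses and the Missing Data paragraph. No new data are needed.
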